4.2.2.3 Restrictions on diet and life style

Grapefruits, Seville oranges and their juices, dietary supplements (including vitamins and garlic supplements) and herbal products are not permitted from 7 days before day 1 and until last PK of the study.

Alcoholic beverages are not permitted from 48 hours prior to and during all visits.

Intake of coffee, tea, chocolate, cola, energy drinks and other methylxanthine-containing drinks or foods and ice-cold beverages are not allowed for a period of 8 hours prior to clinic visits and during in-house confinement at the study site. Decaffeinated beverages are allowed.

Standardised meals will be provided during in-house confinement at the study site. Subjects are restricted from consuming any foods or drinks than those provided by the staff.

Proprietary confidential information © 2017 Boehringer Ingelheim International GmbH or one or more of its affiliated companies

Excessive strenuous physical activity should be avoided for 72 hours prior to screening (Visit 1). Strenuous exercise should be avoided for 48 hours prior to and during all other visits (Visits 2-6).

4.2.2.4 Restrictions regarding women of childbearing potential

Women of childbearing potential are excluded from participation in this study.

4.3 TREATMENT COMPLIANCE

Each subject will be trained in the correct use of the Respimat® inhaler using the training Respimat® inhaler with inserted placebo cartridge. Please refer to [Appendix 10.1](#)

5. VARIABLES AND THEIR ASSESSMENT

5.1 TRIAL ENDPOINTS

[figure not shown]

Figure 5.1: 1 Illustration of endpoints based on spirometry measurements (FEV₁ as example).

The figure displays measurements during one treatment period that is during the baseline bolus challenge prior to drug administration, during drug administration and during the treatment challenge on Day 2.

Proprietary confidential information © 2017 Boehringer Ingelheim International GmbH or one or more of its affiliated companies

In the following baseline refers to the measurement obtained from the baseline bolus MCh challenge prior to administration of trial medication within each period.

5.1.1 Primary Endpoint(s)

The primary endpoint for the study to assess safety of BI 443651 is

- Absolute change from baseline in maximum FEV₁ reduction following MCh challenge.

The primary endpoint will be compared to placebo for each dose level of BI 443651.

For a visualization of the endpoint refer to [Figure 5.1 :1](#), a detailed description of the primary endpoint and the primary statistical analysis is provided in [Section 7](#).

5.1.2 Secondary Endpoint(s)

The following secondary endpoints will be assessed:

- Relative change from baseline in FEV₁ AUC_{0-tz} following bolus MCh challenge
- Time to recovery of FEV₁ to within 95% of post-diluent value

The secondary endpoints will be compared to placebo for each dose level of BI 443651.

For a visualization of the endpoints refer to [Figure 5.1:1](#), a detailed description of the secondary endpoints including statistical analysis is provided in [Section 7](#).

5.2 ASSESSMENT OF EFFICACY

There are no efficacy assessments in this study

5.3 ASSESSMENT OF SAFETY

5.3.1 Physical examination

A physical examination will be performed at Screening (Visit 1) and on completion of the study. A targeted physical examination focussing on heart and lungs will be performed at the start of each treatment period (Visits 2 – 5).

All clinically significant findings at screening (Visit 1) will be recorded on the Medical History/Baseline Conditions in the eCRF.

New clinically significant findings or worsening of screening findings detected at the follow up visit (Visit 6) will be recorded as adverse events on the appropriate eCRF page.

An explanation of the aetiology of clinically significant abnormal physical findings must be made on the eCRF. All relevant (in the opinion of the investigator) abnormal physical findings have to be followed up until normalised or sufficiently characterised.

5.3.2 Vital Signs

Pulse rate, systolic and diastolic blood pressure will be measured and recorded at the screening visit (Visit 1) and at subsequent visits at selected timepoints. Measurements will be obtained with the subject supine and rested for at least 5 minutes.

5.3.3 Safety laboratory parameters

For the assessment of laboratory parameters, blood will be collected by the trial site at the time points indicated in the [Flow Chart](#) after the subjects have fasted for at least 10h (prior to the Screening Visit (Visit 1)) Subjects may drink water during the fasting period.

Subjects do not need to fast prior to laboratory testing at subsequent visits (i.e: after Visit 1)

If safety laboratory measurement is performed at the same time as other blood collection, e.g. PK sampling, safety laboratory measurement will always be performed first, preferably without any tourniquet.

The parameters that will be determined are listed in Table 5.3.3:1 Reference ranges will be provided in the ISF.

Manual differential white blood cell count or urine sediment examination will only be performed if there is an abnormality in the automatic blood cell count or in the urinalysis, respectively.

Table 5.3.3:1 Routine laboratory tests

Category	Test name	A	B
Haematology	Haematocrit Haemoglobin Red blood cells (RBC) White blood cells (WBC) Platelets Reticulocytes	x x x x x x	x x x x x x
Automatic WBC differential (relative and absolute)	Neutrophils Eosinophils Basophils Monocytes Lymphocytes	x x x x x	x x x x x
Manual differential WBC (if automatic differential is abnormal)	Polymorphnuclear neutrophils (segs), band neutrophils (stabs), eosinophils, basophils, monocytes, lymphocytes		
Coagulation	Activated partial thromboplastin time (aPTT) Prothrombin Time (Quick and INR)	x x	x x
Enzymes	Alanine aminotransferase (ALT/GPT, SGPT) Alkaline phosphatase Gamma-glutamyl transferase (GGT) Lactate dehydrogenase	x x x x	x x x x

Proprietary confidential information © 2017 Boehringer Ingelheim International GmbH or one or more of its affiliated companies

	Amylase Lipase	x x	x x
Category	Test name	A	B
Substrates	Glucose (plasma) Creatinine eGFR (calculated from serum creatinine using CKD-EPI formula) Bilirubin, total Bilirubin direct Cholesterol, total Triglycerides C-reactive protein Urea	x x x x x x x x	x x x x x x x x
Electrolytes	Calcium Sodium Potassium Chloride	x x x x	x x x x
Hormones	Thyroid stimulating hormone (TSH)	x	
	Human chorionic gonadotrophin (HCG)	x	
Urinalysis (Stix) [Urin-Sediment will be performed, if urinalysis abnormal]	Urine nitrite Urine protein Urine glucose Urine ketone Urobilinogen Urine bilirubin Urine RBC Urine WBC Urine pH	x x x x x x x x	x x x x x x x x
Urine sediment (microscopic examination if erythrocytes, leukocytes, nitrite or protein are abnormal in urine)	Only positive finding will be reported (for instance, the presence of sediment bacteria, casts in sediment, squamous epithelial cells,		

A: Parameters to be determined at screening examination and during the study (refer to [Flow Chart](#) for time points)

B: Parameters to be determined during the follow-up visit

The laboratory tests will be performed by a central laboratory.

Proprietary confidential information © 2017 Boehringer Ingelheim International GmbH or one or more of its affiliated companies

Instructions for the processing, storage and shipment of samples to the central laboratory will be provided to the site.

Where local laboratory results are also used, central laboratory results will take precedence in the interpretation of the results. Local laboratory results will take precedence for dosing decisions (e.g: K⁺). Local laboratory values will not be entered into the database.

Laboratory data will be transmitted electronically from the central laboratory to the trial site.

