18	Spirometry to be performed pre-MCh challenge, post-diluent and post methacholine dose. Post-methacholine spirometry (FEV ₁ only) timepoints will be relative to the last exhalation of methacholine solution and will be scheduled as single measurements at 30 seconds and 90 seconds, followed by duplicate measurements (FEV1 and FVC) at 5,10, 20, 30,45 minutes, 1.0, 1.25, 1.5, 1.75, 2.0, 2.25, 2.5, 2.75, 3.0, 3.5, 4.0, 4.5, 5.0, 6.0, 7.0 and 8.0 hours
19	Central laboratory: Central laboratory testing (full laboratory screen) will be performed at the screening visit (Visit 1) and on completion of the study (EOT visit / Visit 6). Details of the tests required are provided in Section 5.3.3 .
20	For female subjects: Blood HCG will be performed at screening to confirm eligibility (central laboratory)
21	Electrolytes will be measured prior to start of trial procedures and prior to discharge from the clinic on conclusion of trial procedures at each of the treatment periods (Visits 2 to 5). Initial assessment will be performed by local laboratory. In addition to local testing, a sample for electrolytes will also be sent to the central laboratory.
22	If any significant laboratory test abnormalities are detected, specifically liver function tests, the subject should return to the clinic for repeat testing
23	Spirometry to be performed pre-MCh challenge, post-diluent and post-methacholine dose. Post-methacholine spirometry (FEV ₁) timepoints will be relative to the last exhalation of final methacholine solution and will be scheduled as single measurements at 30 seconds and 90 seconds, followed by duplicate measurements (FEV1 and FVC) at 5, 10, 20, 30, 45 minutes, 1.0, 1.25, 1.5, 1.75, 2.0, 2.25, 2.5, 2.75 and 3.0 hours
24	Must be completed within 30 minutes prior to drug administration
25	FEV ₁ and FVC in triplicate, unless otherwise specified
26	The cumulative times specified in the planned time column are for orientation only. Depending on the actual a.m dosing time at the given day, the procedures and observations related to that a.m dosing (such as pre a.m dose and post a.m dose measurements of the same day) have to be adapted respectively.
27	The end of treatment (EOT) visit should be scheduled no earlier than 14 days after the last dose of study medication. In the event of early discontinuation, an additional earlier visit may be scheduled at investigator discretion.

TABLE OF CONTENTS

CLINICAL TRIAL PROTOCOL.....	1
TITLE PAGE.....	1

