Medical and scientific judgement should be exercised in deciding whether other situations should be considered serious reactions, such as important medical events that might not be immediately life threatening or result in death or hospitalisation but might jeopardise the patient or might require intervention to prevent one of the other outcomes listed above. Examples of such events are intensive treatment in an emergency room or at home for allergic bronchospasm, blood dyscrasias or convulsions that do not result in hospitalisation or development of dependency or abuse. Any suspected transmission via a medicinal product of an infectious agent is also considered a serious adverse reaction.

Aes considered “Always Serious”

Cancers of new histology and exacerbations of existing cancer must be reported as a serious event regardless of the duration between discontinuation of the drug and the occurrence of the cancer.

In accordance with the European Medicines Agency initiative on Important Medical Events, Boehringer Ingelheim has set up a list of further Aes, which by their nature, can always be considered to be “serious” even though they may not have met the criteria of an SAE as given above.

The latest list of “Always Serious Aes” can be found in the RDC system.

Adverse events of special interest (AESIs)

The term AESI relates to any specific AE that has been identified at the project level as being of particular concern for prospective safety monitoring and safety assessment within this trial, e.g. the potential for Aes based on knowledge from other compounds in the same class. AESI need to be reported to the sponsor’s Pharmacovigilance Department within the same timeframe that applies to SAE, please see above.

The following are considered as AESIs:

Hepatic injury

A hepatic injury is defined by the following alterations of hepatic laboratory parameters:

- an elevation of AST and/or ALT ≥ 3 fold ULN combined with an elevation of total bilirubin ≥ 2 fold ULN measured in the same blood draw sample, and/or
- marked peak aminotransferase (ALT, and/or AST) elevations ≥ 10 fold ULN

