These laboratory findings constitute a hepatic injury alert and the patients showing these lab abnormalities need to be followed up according to the “DILI checklist” provided in RDC. In case of clinical symptoms of hepatic injury (icterus, unexplained encephalopathy, unexplained coagulopathy, right upper quadrant abdominal pain, etc.) without lab results (ALT, AST, total bilirubin) available, the Investigator should make sure these parameters are analysed, if necessary in an unscheduled blood test. Should the results meet the criteria of hepatic injury alert, the procedures described in the DILI checklist should be followed.

Intensity of Aes

The intensity of the AE should be judged based on the following:

Mild:	Awareness of sign(s) or symptom(s) that is/are easily tolerated
Moderate:	Enough discomfort to cause interference with usual activity
Severe:	Incapacitating or causing inability to work or to perform usual activities

Causal relationship of Aes

The definition of an adverse reaction implies at least a reasonable possibility of a causal relationship between a suspected medicinal product and an adverse event. An adverse reaction, in contrast to an adverse event, is characterised by the fact that a causal relationship between a medicinal product and an occurrence is suspected.

Medical judgment should be used to determine the relationship, considering all relevant factors, including pattern of reaction, temporal relationship, de-challenge or re-challenge, confounding factors such as concomitant medication, concomitant diseases and relevant history.

Arguments that may suggest that there is a reasonable possibility of a causal relationship could be:

- The event is consistent with the known pharmacology of the drug
- The event is known to be caused by or attributed to the drug class.
- A plausible time to onset of the event relative to the time of drug exposure.
- Evidence that the event is reproducible when the drug is re-introduced
- No medically sound alternative aetiologies that could explain the event (e.g. pre-existing or concomitant diseases, or co-medications).

Proprietary confidential information © 2017 Boehringer Ingelheim International GmbH or one or more of its affiliated companies

- The event is typically drug-related and infrequent in the general population not exposed to drugs (e.g. Stevens-Johnson syndrome).

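### AST is named in both hepatic-injury AESI criteria but is missing from the scheduled laboratory panel, so an asymptomatic rise in AST alone would go undetected

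*Protocol*

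**What the plan says.** Protocol Section 5.3.6.1 lists hepatic injury as the only AESI and gives two laboratory criteria. The first is "an elevation of AST and/or ALT ≥ 3 fold ULN combined with an elevation of total bilirubin ≥ 2 fold ULN", both measured in the same blood draw. The second is "marked peak aminotransferase (ALT, and/or AST) elevations ≥ 10 fold ULN". For a subject with clinical symptoms of hepatic injury "without lab results (ALT, AST, total bilirubin) available, the Investigator should make sure these parameters are analysed", by an unscheduled test if need be.

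On what is measured, Section 5.3.3 states: "The parameters that will be determined are listed in Table 5.3.3:1". The Enzymes entry in that table reads "Alanine aminotransferase (ALT/GPT, SGPT) Alkaline phosphatase Gamma-glutamyl transferase (GGT) Lactate dehydrogenase", with amylase and lipase after the page break. Total and direct bilirubin are listed under Substrates. AST does not appear under any name.

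On when it is measured, flow chart note 19 says: "Central laboratory testing (full laboratory screen) will be performed at the screening visit (Visit 1) and on completion of the study". Note 21 schedules electrolytes only at Visits 2 to 5. The table's footnote describes its first column more broadly: "A: Parameters to be determined at screening examination and during the study".

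On use, Section 5.3.6.1 puts AESIs on the same reporting timeline as serious adverse events, and SAP Section 7.8.1 gives subjects with AESIs their own table, referring back to the protocol for the definition.

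**The concern.** A definition that turns on a laboratory value needs that value to be measured. Here each criterion can be met by either of two aminotransferases, and the panel supplies one. A subject whose AST crosses a threshold while ALT stays below it meets the AESI definition, but nothing in the scheduled data would show it.

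Protocol Section 2.3 commits the trial to timely detection and follow-up of changes in selected liver parameters and refers to Section 5.3.6.1, the section that names AST. At stake are the expedited reporting and follow-up that an AESI brings, and the reading of the AESI table. A count of zero would rest on ALT and bilirubin, plus whatever AST values unscheduled testing happened to produce, and the table as planned has nothing to tell the reader so.

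**Working it through.** No sample size, power or event rate is involved. The check sets the definition, the panel and the schedule side by side and then asks whether the missing row could be an artefact of reading the PDF.

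**1. Definition against panel**

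| Analyte used by the AESI | Criterion 1 | Criterion 2 | In Table 5.3.3:1 |
|---|---|---|---|
| ALT | yes | yes | yes (Enzymes, A and B) |
| AST | yes | yes | no |
| Total bilirubin | yes | not used | yes (Substrates, A and B) |

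AST is named in 2 of 2 criteria and has 0 entries in the panel.

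**2. Panel against schedule**

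- Visit 1: full panel, before any study drug. No AST.
- Visits 2 to 5: electrolytes only. No AST, ALT or bilirubin.
- Visit 6: full panel, at least 14 days after the last dose (flow chart note 27). No AST.

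Scheduled draws that yield AST: 0. Scheduled draws after first dosing that yield ALT and bilirubin: 1 (Visit 6).

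**3. Other routes to an AST value**

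- The unscheduled test in Section 5.3.6.1 depends on clinical symptoms of hepatic injury with no results available.
- Flow chart note 22 asks for repeat testing once a significant abnormality, liver tests in particular, has been detected. For AST that presupposes an AST result.
- The SAP contains no analyte list that adds AST.

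An AST-only rise without symptoms passes through all three. If AST is measured off schedule, there is no screening value to compare it with.

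**4. Could a table row have been lost?** The Enzymes entry shows 4 names with 4 marks in each column, then 2 names with 2 marks in each column: 6 tests and 6 marks. A dropped name would normally leave a spare mark, and there is none. The count is not perfectly reliable. Substrates and Urinalysis each show 9 names against 8 marks per column, but there the marks fall short of the names, which is the opposite of what a lost name would leave. A lost name and mark together cannot be excluded, though nothing points to one.

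**5. Size of the change.** Minimum subjects: 4 (Part 1) + 32 (Part 2) = 36. Full-panel visits: 2. Assays: 36 × 2 = 72. This is a floor, because enrolment is at least 36, non-completers are replaced (Section 3.3.5), and screen failures also give a Visit 1 sample.

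**The case against.** The strongest case on the other side is that little is lost.

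- **The AESI still works through ALT.** Both criteria read as and/or, and ALT and total bilirubin are in the panel. This stands. A reader might infer that hepatic injury cannot be assessed at all, but the documents do not support that. Only the AST-only case is lost, and the documents give no rate for it.
- **There is a fallback.** Section 5.3.6.1 calls for AST when symptoms appear without results. This stands too, so it would be wrong to say that AST can never be obtained. The fallback does not reach the subject without symptoms.
- **No endpoint is affected.** A reader might infer that a safety endpoint has become unevaluable. The primary and secondary endpoints in Section 5.1 are all based on FEV1, hepatic injury is an adverse-event category summarised descriptively, and no withdrawal or trial-stopping criterion in Section 3.3.4 names AST.
- **Liver injury is not the expected toxicity.** Section 2.3 identifies serum electrolytes, potassium above all, as the potential systemic toxicity and treats liver injury as a rare, general concern. That bears on priority. It does not remove the mismatch.
- **The remedy adds little.** Screening precedes treatment and cannot show a treatment-emergent case, and Visit 6 is late. This is correct and limits the gain.

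A reader might also infer that the AESI table will be presented as if the full definition had been applied. The SAP only points to the protocol definition, so how the table would be annotated is unknown.

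**Conclusion.** The inconsistency holds, in limited form. Followed as written, the plan cannot apply its own AESI definition in full to any scheduled sample. The consequence is confined to an AST-only elevation in a subject without symptoms, and to the absence of a screening AST value for interpreting any unscheduled result. It affects all subjects (at least 36) in both parts. It does not touch the primary or secondary analyses or any stopping rule.

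The conclusion rests on two assumptions: that Table 5.3.3:1 as read is complete, which the matching counts support but do not prove, and that the DILI checklist and the investigator site file, which are not in the documents, do not add AST to the scheduled tests. It should be corrected because the correction is cheap, but it is not a critical flaw.

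**What to change.** Reconcile the panel with the definition. Add AST to the Enzymes row of Table 5.3.3:1, columns A and B, so that it is measured on blood already drawn at Visits 1 and 6. The cost is one edited table row and at least 72 assays, more with screen failures and replacements, with no new visit or sampling time.

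If AST was left out on purpose, state in Section 5.3.6.1, and in a footnote to the AESI table planned in SAP Section 7.8.1, that AST comes only from unscheduled testing. That costs two sentences.

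Either way, reconcile the column A footnote, which promises the parameters during the study, with flow chart notes 19 and 21, which schedule the full panel only at Visits 1 and 6 and electrolytes alone at Visits 2 to 5. Adding AST buys a baseline and one post-dose value per subject. It does not provide liver monitoring close to dosing, since ALT and bilirubin are not scheduled there either.

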5.3.4 Electrocardiogram

A standard 12-lead ECG will be performed on all subjects at the screening visit (Visit 1) and during treatment period (Visits 2-5). ECG will be performed with the subject supine and rested for at least 5 minutes. At Visit 1, significant findings must be recorded on the Medical History/Baseline Condition page. Any clinically relevant (according to the investigator's opinion) changes in the ECG during the study (after Visit 1) should be documented on the AE page of the eCRF.

5.3.5 Other safety parameters

Not applicable

5.3.6 Assessment of adverse events

5.3.6.1 Definitions of Aes

Adverse event

An adverse event (AE) is defined as any untoward medical occurrence in a patient or clinical investigation subject administered a medicinal product and which does not necessarily have to have a causal relationship with this treatment.

An AE can therefore be any unfavourable and unintended sign (including an abnormal laboratory finding), symptom, or disease temporally associated with the use of a medicinal product, whether or not considered related to the medicinal product.

Adverse reaction

An adverse reaction is defined as a response to a medicinal product which is noxious and unintended. Response in this context means that a causal relationship between a medicinal product and an adverse event is at least a reasonable possibility. Adverse reactions may arise from use of the product within or outside the terms of the marketing authorisation or from occupational exposure. Conditions of use outside the marketing authorization include off-label use, overdose, misuse, abuse and medication errors.

Serious adverse event

A serious adverse event (SAE) is defined as any AE which:

- results in death,
- is life-threatening, this refers to an event in which the patient was at risk of death at the time of the event; it does not refer to an event that hypothetically might have caused death if more severe.
- requires inpatient hospitalisation or
- prolongation of existing hospitalisation,
- results in persistent or significant disability or incapacity, or
- is a congenital anomaly / birth defect,
or
- is to be deemed serious for any other reason if it is an important medical event when based upon appropriate medical judgment which may jeopardise the patient and may require medical or surgical intervention to prevent one of the other outcomes listed in the above definitions.

Medical and scientific judgement should be exercised in deciding whether other situations should be considered serious reactions, such as important medical events that might not be immediately life threatening or result in death or hospitalisation but might jeopardise the patient or might require intervention to prevent one of the other outcomes listed above. Examples of such events are intensive treatment in an emergency room or at home for allergic bronchospasm, blood dyscrasias or convulsions that do not result in hospitalisation or development of dependency or abuse. Any suspected transmission via a medicinal product of an infectious agent is also considered a serious adverse reaction.

Aes considered “Always Serious”

Cancers of new histology and exacerbations of existing cancer must be reported as a serious event regardless of the duration between discontinuation of the drug and the occurrence of the cancer.

In accordance with the European Medicines Agency initiative on Important Medical Events, Boehringer Ingelheim has set up a list of further Aes, which by their nature, can always be considered to be “serious” even though they may not have met the criteria of an SAE as given above.

The latest list of “Always Serious Aes” can be found in the RDC system.

Adverse events of special interest (AESIs)

The term AESI relates to any specific AE that has been identified at the project level as being of particular concern for prospective safety monitoring and safety assessment within this trial, e.g. the potential for Aes based on knowledge from other compounds in the same class. AESI need to be reported to the sponsor’s Pharmacovigilance Department within the same timeframe that applies to SAE, please see above.

The following are considered as AESIs:

Hepatic injury

A hepatic injury is defined by the following alterations of hepatic laboratory parameters:

- an elevation of AST and/or ALT ≥ 3 fold ULN combined with an elevation of total bilirubin ≥ 2 fold ULN measured in the same blood draw sample, and/or
- marked peak aminotransferase (ALT, and/or AST) elevations ≥ 10 fold ULN

These laboratory findings constitute a hepatic injury alert and the patients showing these lab abnormalities need to be followed up according to the “DILI checklist” provided in RDC. In case of clinical symptoms of hepatic injury (icterus, unexplained encephalopathy, unexplained coagulopathy, right upper quadrant abdominal pain, etc.) without lab results (ALT, AST, total bilirubin) available, the Investigator should make sure these parameters are analysed, if necessary in an unscheduled blood test. Should the results meet the criteria of hepatic injury alert, the procedures described in the DILI checklist should be followed.

Intensity of Aes

The intensity of the AE should be judged based on the following:

Mild:	Awareness of sign(s) or symptom(s) that is/are easily tolerated
Moderate:	Enough discomfort to cause interference with usual activity
Severe:	Incapacitating or causing inability to work or to perform usual activities

Causal relationship of Aes

The definition of an adverse reaction implies at least a reasonable possibility of a causal relationship between a suspected medicinal product and an adverse event. An adverse reaction, in contrast to an adverse event, is characterised by the fact that a causal relationship between a medicinal product and an occurrence is suspected.

Medical judgment should be used to determine the relationship, considering all relevant factors, including pattern of reaction, temporal relationship, de-challenge or re-challenge, confounding factors such as concomitant medication, concomitant diseases and relevant history.

Arguments that may suggest that there is a reasonable possibility of a causal relationship could be:

- The event is consistent with the known pharmacology of the drug
- The event is known to be caused by or attributed to the drug class.
- A plausible time to onset of the event relative to the time of drug exposure.
- Evidence that the event is reproducible when the drug is re-introduced
- No medically sound alternative aetiologies that could explain the event (e.g. pre-existing or concomitant diseases, or co-medications).

Proprietary confidential information © 2017 Boehringer Ingelheim International GmbH or one or more of its affiliated companies

- The event is typically drug-related and infrequent in the general population not exposed to drugs (e.g. Stevens-Johnson syndrome).
- An indication of dose-response (i.e. greater effect size if the dose is increased, smaller effect size if dose is diminished).

Arguments that may suggest that there is no reasonable possibility of a causal relationship could be:

- No plausible time to onset of the event relative to the time of drug exposure is evident (e.g. pre-treatment cases, diagnosis of cancer or chronic disease within days / weeks of drug administration; an allergic reaction weeks after discontinuation of the drug concerned)
- Continuation of the event despite the withdrawal of the medication, taking into account the pharmacological properties of the compound (e.g. after 5 half-lives). Of note, this criterion may not be applicable to events whose time course is prolonged despite removing the original trigger.
- Additional arguments amongst those stated before, like alternative explanation (e.g. situations where other drugs or underlying diseases appear to provide a more likely explanation for the observed event than the drug concerned).
- Disappearance of the event even though the study drug treatment continues or remains unchanged.

